8.2. Analysis of the Primary Efficacy Endpoint

The proportion of subjects in each treatment group who reach the study endpoint of treatment failure by 28 days will be compared to placebo using Fisher's Exact 2-sided test of proportions. Additionally, the frequency for each outcome (intubation, ECMO, death) will be determined within each group. The ITT, mITT and PP analysis populations will be used to analyze the primary endpoint.

8.3. Definition of the Exploratory Efficacy Endpoints

Exploratory endpoints include the following which will be summarized using the PP populations by treatment group received:

- Assess the number of days of hospitalization relative to treatment group
- Assess the number of days requiring ICU care relative to treatment group. If a subject does not require ICU care, the number of days will be set to zero for the group summary. The number of ICU days will be summarized for all subjects in each group and for the proportion of those who are actually in ICU.
- Assess the number of days of non-invasive or mechanical ventilation relative to treatment group. If a subject does not require non-invasive or mechanical ventilation, the number of days will be set to zero for the group summary. The number of mechanical ventilation

CONFIDENTIAL Page 11 03DEC2021

days will be summarized for all subjects in each group and for the proportion of those who are actually on mechanical ventilation.

- Assess incidence of WHO COVID-19 Classification levels relative to baseline serum IL-6 level
- Assess incidence of WHO COVID-19 Classification levels relative to baseline serum ferritin level
- Assess incidence of WHO COVID-19 Classification levels relative to baseline CRP
- Assess trough level of GLS-1027 relative to serum creatinine
- Assess the maximal level of Positive End-Expiratory Pressure (PEEP) for subjects who are intubated relative to treatment group.
- Assess the number of days of PEEP > 5 cm H2O for subjects who are intubated relative to treatment group
- Assessment of WHO COVID-19 Classification at 28 day relative to treatment group
- Assess SARS-CoV-2 IgM antibody responses relative to treatment group

No adjustments or imputations will be made for deaths or other forms of missingness except those already described above.

Corticosteroids will be recorded as a prior or concomitant medication. Subgroup analysis will be performed to compare outcomes relative to treatment group and relative to use or non-use of corticosteroids. Primary treatment outcomes will be determined from the time of enrollment through to Day 28.

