2. HYPOTHESIS AND STUDY OBJECTIVES

2.1 Hypothesis

GLS-1027 will be safe, well tolerated and, for those admitted to hospital with PCR confirmed SARS-CoV-2 infection at WHO COVID-19 classification level of 3 or 4, will reduce likelihood for progression to WHO COVID-19 classification level of 6 or greater (defined as severe pneumonitis characterized by the need for intubation with mechanical ventilation, initiation of ECMO, or death) or need for salvage treatment started 72 hours after study entry with either an IL-6 monoclonal antibody or dexamethasone at a dose of $\geq 6 \text{ mg/day}$.

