4.5 Treatment with dexamethasone post-enrollment

Treatment with dexamethasone at a dose of 6 mg/day for 10 days is currently considered as part of the standard of care for COVID-19 at many institutions, however, the specifics of treatment and whether such treatment is formally algorithm based varies between institutions. Moreover, it is recognized that dexamethasone treatment may be ordered as part of clinical care for some subjects after enrollment into the study.

Enrollment into the study is allowed for individuals who have not been treated with dexamethasone since hospital admission. Enrollment into the study is also allowed for those have received a single bolus dose of 6 mg of dexamethasone at presentation to the hospital with or without continuation of dexamethasone at a dose of 3.5 mg/day or less.

Enrolled subjects for whom dexamethasone is initiated within 72 hours of the time of 1st dose of study drug will be considered to have required dexamethasone at the time of presentation to hospital and will be treated the same as those who received a single bolus dose of 6 mg at presentation to the hospital. Unless dexamethasone is prescribed for 10 days at 6 mg, sSuch subjects will not be considered to have met the definition of the need for salvage therapy, and will not be considered as meeting a study endpoint for failure.

Enrolled subjects for whom dexamethasone is ordered at a dose of ≥ 6 mg per day and is initiated 72 hours or later after the 1st dose of study drug will be considered to have met the definition of need for salvage therapy and thus have met a study endpoint for failure. Initiation of treatment with dexamethasone at a dose of less than 6 mg/day after enrollment in the study will not be considered as treatment failure.

Subjects will be subgrouped for summary by concomitant bolus dexamethasone within 72 hours of enrollment versus no concomitant dexamethasone with 72 hours of enrollment.

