3. STUDY DESIGN AND PLAN

This is a Phase II, randomized, double-blind, placebo-controlled study to assess 2 dose levels of GLS-1027 for the prevention of treatment failure among participants admitted to the hospital with PCR confirmed infection with SARS-CoV-2 (WHO classification 3 or 4). Subjects can be enrolled up to 72 hours from the time of hospital admission.

Participants will be randomized to placebo or GLS-1027 at either 120 mg or 360 mg daily in a 1:1:1 ratio as adjunctive to standard of care based on the hospital COVID-19 treatment algorithm and/or local COVID-19 treatment practices. Participants will be administered study drug for a maximum treatment period of 14 days or until discharge or death, whichever comes first. Primary outcome will be assessment at day 28, with follow-up to continue to Day 56 to document AEs and outcome as to discharge, death, or WHO COVID-19 classification level if subject remains hospitalized.

All subjects will be considered to have completed the study except for the following circumstances:

- Withdrawal of consent from study
- Loss to follow-up
- Stopped study treatment for any reason other than discharge, pregnancy, or decreased renal function

Table 1: Schedule of Assessments

Tests and Observations	1	2	3	4	5	6	7	8	9	10	11	12	13	14	15	28	56 ^m
Clinical Evaluations																	
Obtain written Informed Consent	Х																
Confirm Eligibility Criteria	Х																
Demographics	Х																
Medical History	Х																
Concomitant Medications	Х	Х	Х	Х	Х	Х	Х	Х	Х	Х	Х	Х	Х	Х	Х	Х	Х
Review Medical Record	Х	Х	Х	Х	Х	Х	Х	Х	Х	Х	Х	Х	Х	Х	Х	Х	Х
WHO COVID-19 Classification (Appendix B)	Х	Х	Х	Х	Х	Х	Х	Х	Х	Х	Х	Х	Х	Х	Х	Х	Х
Safety Evaluations																	
Record Adverse Events	Х	Х	Х	Х	Х	Х	Х	Х	Х	Х	Х	Х	Х	Х	Х	Х	Х
Record AM Vital Signs a	Х	Х	X	Х	Х	Х	Х	Х	Х	Х	Х	Х	Х	Х	Х		
Record Hematology ^b	Х	Х	Х			Х			Х			Х			Х		
Record Basic Metabolic Panel ^c	Х	Х	Х	Х	Х	Х	Х	Х	Х	Х	Х	Х	Х	Х	Х		
Record liver function studies (LFTs) °	Х					Х			Х			Х			Х		
Record other labs ^d (for days available)	Х	Х	Х	Х	Х	Х	Х	Х	Х	Х	Х	Х	Х	Х	Х		
Record Procalcitonin (baseline value) e	Х																
Record admission CXR	Х																
Record if care given in ICU setting	Х	Х	Х	Х	Х	Х	Х	Х	Х	Х	Х	Х	Х	Х	Х		
Record whether nasal O ₂ prescribed and dose level (L/min) ^f	Х	Х	Х	Х	Х	Х	Х	Х	Х	Х	Х	Х	Х	Х	Х		
Record whether CPAP prescribed and expiratory pressure ⁹	X	X	X	X	Х	Х	X	Х	Х	X	Х	Х	X	Х	X		

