7.5. Prior and Concomitant Medications

A prior medication is defined as a medication that was administered up to 4 months prior to time of enrollment. All other medications will be considered concomitant.

Medication verbatim names collected from the CRF will be mapped to Anatomical Therapeutic Chemical (ATC) Classes and Preferred Names using the World Health Organization's WHODrug Global March 2020 version. Preferred Names will consist of only the base compounds and not the salts (e.g., Naproxen Sodium will be listed only as Naproxen). Concomitant medications will be summarized for each treatment by ATC class and preferred name. Prior and concomitant medications will be listed.

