(ITT Population)

ATC Class	GLS-1027	GLS-1027	Placebo
Preferred Name	120 mg	360 mg	(N=XX)
	(N=XX)	(N=XX)	
Subjects who received any prior or concomitant			
medications	x (xx.x%)	x (xx.x%)	x (xx.x%)
Subjects who received any prior or concomitant corticosteroids	x (xx.x%)	x (xx.x%)	x (xx.x%)
ATC Class # 1>	x (xx.x%)	x (xx.x%)	x (xx.x%)
<preferred #1="" name=""></preferred>	x (xx.x%)	x (xx.x%)	x (xx.x%)
<preferred #2="" name=""></preferred>	x (xx.x%)	x (xx.x%)	x (xx.x%)
<preferred #3="" name=""></preferred>	x (xx.x%)	x (xx.x%)	x (xx.x%)
<atc #="" 2="" class=""></atc>	x (xx.x%)	x (xx.x%)	x (xx.x%)
<preferred #1="" name=""></preferred>	x (xx.x%)	x (xx.x%)	x (xx.x%)
<preferred #2="" name=""></preferred>	x (xx.x%)	x (xx.x%)	x (xx.x%)
<preferred #3="" name=""></preferred>	x (xx.x%)	x (xx.x%)	x (xx.x%)
•	, ,	. ,	, ,
•			

A concomitant medication is any medication that was ongoing or started on or after the date of first dose. A prior medication is defined as a medication that was administered up to 4 months prior to time of enrollment.

Medications are coded using WHODrug Global (March 2020) and ordered by descending order of overall incidence of ATC class and overall incidence of preferred name within each class. At each level of summation (overall, ATC class, preferred name), subjects reporting more than one medication are counted only once.

Reference: Listing 16.2.4.3

Programming Note: Sort table by descending overall count of ATC class and descending overall count of preferred name within each class.

Table 14.1.5
Treatment Exposure

	(Cafaty Danulation)		
	(Safety Population)	CLC 1027	
	GLS-1027	GLS-1027	
	120 mg	360 mg (N=XX)	Placebo (N=XX)
	(N=XX)		
Duration of exposure (days) [1]			
n	XX	xx	XX
Mean (SD)	xx.x (xx.xx)	xx.x (xx.xx)	xx.x (xx.xx)
Median	xx.x	xx.x	xx.x
Min, Max	xx, xx	XX, XX	XX, XX
Total number of doses taken			
n	XX	xx	XX
Mean (SD)	xx.x (xx.xx)	xx.x (xx.xx)	xx.x (xx.xx)
Median	XX.X	xx.x	xx.x
Min, Max	xx, xx	xx, xx	xx, xx
Total number of doses missed			
n	XX	xx	XX
Mean (SD)	xx.x (xx.xx)	xx.x (xx.xx)	xx.x (xx.xx)
Median	xx.x	xx.x	xx.x
Min, Max	xx, xx	xx, xx	XX, XX

^[1] Duration of exposure is defined as the date of last dose minus the date of first dose + 1. Reference: Listing 16.2.5.1.

Table 14.2.1.1

Analysis of Overall Treatment Failure
(ITT Population)

Overall/Subjects with prior or concomitant corticosteroids/Subjects without prior or concomitant corticosteroids

	GLS-1027	GLS-1027	Placebo (N=XX)	
	120 mg	360 mg		
	(N=XX)	(N=XX)		

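### The corticosteroid subgroup counts steroids started after randomisation, so its by-arm treatment failure rates are not protected by randomisation

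*SAP*

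**What the plan says.** The last paragraph of SAP 8.3 treats corticosteroids as follows: "a prior or concomitant medication. Subgroup analysis will be performed to compare outcomes relative to treatment group and relative to use or non-use". It gives no time limit for what counts as use.

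The shell for Table 14.2.1.1 turns this into three sets of pages, headed "Overall/Subjects with prior or concomitant corticosteroids/Subjects without prior or concomitant corticosteroids". Each set shows treatment failure and its components by arm, and programming notes repeat the layout for the mITT and PP populations. P-values are suppressed on the two corticosteroid pages.

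Two SAP definitions decide who is a user. SAP 7.5 defines a prior medication as one "administered up to 4 months prior to time of enrollment. All other medications will be considered concomitant". The footnote to Table 14.1.4 reads: "A concomitant medication is any medication that was ongoing or started on or after the date of first dose". Neither sets a last date. SAP Section 3 states: "Primary outcome will be assessment at day 28, with follow-up to continue to Day 56", and SAP Table 1 collects concomitant medications at both of those visits.

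Protocol 4.5 describes a different split: "Subjects will be subgrouped for summary by concomitant bolus dexamethasone within 72 hours of enrollment", against no dexamethasone in that window.

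**The concern.** A subgroup comparison of arms keeps the protection of randomisation only if membership is fixed before treatment can influence it. Here it is not. The group of users pools patients already on a steroid at entry with patients given one later, including those given one because they were deteriorating. Nothing in the definitions excludes a steroid started after failure, or after the Day 28 endpoint.

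The protocol gives reason to expect such starts. Section 4.5 accepts that "dexamethasone treatment may be ordered as part of clinical care for some subjects after enrollment into the study". Section 2.1 hypothesises that the drug lowers the "need for salvage treatment started 72 hours after study entry with either an IL-6 monoclonal antibody or dexamethasone" at or above a stated dose. The grouping variable is thus one that the sponsor expects treatment to change.

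Two misreadings follow. If the drug alters steroid prescribing, the printed rates can differ between arms with no effect on failure. If the drug works equally in everyone, the rates can suggest that benefit depends on steroid use. This is the only subgroup display of treatment failure in the SAP shells, and it carries no caution. A drug that changes neither failure nor prescribing gives an expected gap of zero.

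**Working it through.** The plan gives no figure for this subgroup, so there is none to reproduce. Failure rates of 50% (placebo) and 25% (active), with 44 per arm, come from Protocol 8.2. All steroid rates below are assumptions. A steroid start is not itself counted as failure, because SAP 8.1 does not name steroids.

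**A. Uniform benefit, same prescribing rule in both arms.** Let f be the failure rate, b baseline steroid use (independent of failure), and sF and sN the share of the remaining patients who start later among failures and non-failures. Put uF = b + (1-b)sF and uN = b + (1-b)sN.

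- Failure in users = f·uF / [f·uF + (1-f)·uN]
- Failure in non-users = f(1-sF) / [f(1-sF) + (1-f)(1-sN)]

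For b = 0.4, sF = 0.8, sN = 0.1: uF = 0.88 and uN = 0.46.
- Users: placebo 0.44/0.67 = 65.7%; active 0.22/0.565 = 38.9%.
- Non-users: placebo 0.10/0.55 = 18.2%; active 0.05/0.725 = 6.9%.

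| b | sF / sN | Users: placebo, active (difference) | Non-users: placebo, active (difference) |
|---|---|---|---|
| 0.4 | 0.8 / 0.1 | 65.7, 38.9 (-26.7) | 18.2, 6.9 (-11.3) |
| 0.4 | 0.5 / 0.1 | 60.3, 33.7 (-26.7) | 35.7, 15.6 (-20.1) |
| 0.4 | 0.5 / 0.3 | 54.7, 28.7 (-26.0) | 41.7, 19.2 (-22.4) |
| 0.2 | 0.8 / 0.1 | 75.0, 50.0 (-25.0) | 18.2, 6.9 (-11.3) |
| 0.4 | 0.3 / 0.3 | 50.0, 25.0 (-25.0) | 50.0, 25.0 (-25.0) |

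Over b from 0.2 to 0.6, sF from 0.5 to 0.8 and sN from 0.1 to 0.3, the reduction is 25.0 to 26.8 points in users and 11.3 to 22.4 in non-users. The relative risks are 0.51 to 0.67 and 0.38 to 0.46, against a true 0.50. A split on baseline use gives 25 points in both strata.

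**B. No effect on failure, drug changes prescribing.** In both arms half the patients are severe (80% fail) and half mild (20% fail), so overall failure is 50%. With steroid use us in severe and um in mild patients, failure in users = (0.8us + 0.2um)/(us + um); for non-users replace us and um by 1-us and 1-um. Placebo us/um = 0.9/0.5 gives 58.6% in users and 30.0% in non-users.

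| Active us/um | Users (active minus placebo) | Non-users (active minus placebo) |
|---|---|---|
| 0.7 / 0.1 | 72.5 (+13.9) | 35.0 (+5.0) |
| 0.8 / 0.4 | 60.0 (+1.4) | 35.0 (+5.0) |
| 0.7 / 0.5 | 55.0 (-3.6) | 42.5 (+12.5) |
| 0.6 / 0.5 | 52.7 (-5.8) | 46.7 (+16.7) |
| 0.9 / 0.3 | 65.0 (+6.4) | 27.5 (-2.5) |
| 0.9 / 0.5 | 58.6 (0) | 30.0 (0) |

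**C. A second model with no effect on failure.** Failure is 50% in both arms, a share q of failures receive a steroid in either arm, and non-failures receive one at rate g = 0.6 on placebo and 0.3 on active. Failure in users = q/(q+g); in non-users = (1-q)/[(1-q)+(1-g)].
- q = 0.60: users 50.0% vs 66.7% (+16.7); non-users 50.0% vs 36.4% (-13.6).
- q = 0.95: users 61.3% vs 76.0% (+14.7); non-users 11.1% vs 6.7% (-4.4).
- Equal g in both arms gives 0 in both strata.

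B and C are selected cases, not bounds. Together they show that the sign can go either way in each stratum.

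**The case against.** **Exploratory, without p-values, primary comparison untouched.** All true. The consequence is confined to how printed percentages are read. Leaving out p-values does not remove bias from those percentages.

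**The distortion is within sampling noise.** For the first case in B, users number 44 × 0.70 = 30.8 on placebo and 44 × 0.40 = 17.6 on active. The standard error of the gap is √(0.586×0.414/30.8 + 0.725×0.275/17.6) = 13.9 points. Across B the standard errors are about 13 to 14 points in users and 16 to 18 in non-users, so every gap is about one standard error or less. This stands and limits the weight of the point. Bias and imprecision are still separate: noise does not make the split interpretable.

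**Illustration A depends on scale.** The odds ratio is 0.33 in both strata throughout. This also stands, but the shell prints rates, from which readers will take differences or ratios.

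**The argument mixes documents.** The SAP cites protocol version 5.0 and a 14-day treatment period. The protocol reviewed here has 28 days and may be another version, so the departure from its section 4.5 may not apply to version 5.0. Under its section 8.6, late dexamethasone is itself a failure, which A to C do not model. That rule would make matters worse. With 30% on steroids at baseline, 20% of the rest starting late (0.14 of all patients) and 25% failing otherwise, users fail at (0.30×0.25 + 0.14)/0.44 = 48.9% against 25.0% in non-users, partly by definition. The central defect lies wholly within the SAP.

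**Other outputs help.** Listing 16.2.4.3 flags prior corticosteroids, and Table 14.1.4 shows prior or concomitant steroid use by arm. Neither separates starts after randomisation from use ongoing at entry.

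**Conclusion.** The concern holds. As written, the SAP forms its corticosteroid strata partly from events after randomisation and prints failure rates by arm within them. The reading rests on SAP 7.5, 8.3 and the table shells and does not depend on the protocol version. The size and direction of the effect cannot be derived from the documents; the figures above depend on assumed steroid rates. The overall treatment failure comparison, with the high dose tested first, is not affected. The split should be corrected because the change is cheap and an unlabelled table invites a wrong conclusion. It does not threaten the trial's main result. The 72-hour window in Protocol 4.5 also extends past randomisation, so adopting it would narrow the problem without removing it.

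**What to change.** In SAP 8.3 and the headers of Table 14.2.1.1 and its repeats, define the subgroup as systemic corticosteroid use that started before randomisation and was either ongoing at randomisation or given since hospital admission.

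- Derive it from the start date, end date and route in Listing 16.2.4.3 and the randomisation date in Listing 16.2.1.
- State a rule for starts on the randomisation date, since these columns hold dates without times.
- Show as unknown any subject whose start date is imputed to the day of study drug administration under SAP Appendix A, unless the CRF records use before enrolment.
- Say how this subgroup relates to the one in Protocol 4.5, and reconcile the two in the governing protocol version.
- Report corticosteroid starts after randomisation by arm, as a descriptive post-baseline outcome.
- If the any-use split is kept, add a footnote that it includes use started after randomisation and does not estimate the drug's effect with or without steroids.

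The cost is SAP wording, one derivation with its date rules, a short descriptive output and, if needed, a footnote. The CRF was not available, so whether it holds the admission date and steroid use before enrolment must be checked. The baseline-steroid stratum may be small, and the table remains descriptive.

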8.4. Analysis of the Exploratory Efficacy Endpoints

PEEP values during intubation will be plotted separately by treatment over time. Assessment of WHO COVID-19 Classification at 28 day relative to treatment group is discussed in Sections 8.1 and 8.2. Shift tables for worst (most extreme) values of serum IL-6 level, serum ferritin level, and CRP relative to baseline will be presented for each WHO COVID-19 Classification level.

The number of days in ICU, requiring mechanical ventilation and of PEEP > 5 cm H₂O will be summarized by treatment using descriptive statistics (sample size, mean, median, SD, minimum, maximum).

The number and percentage of subjects will be summarized by treatment according to their SARS-CoV-2 IgM antibody response. The above exploratory endpoint analyses will be presented for the PP population and individual results will be listed by treatment and study day. No formal statistical analysis is planned.

CONFIDENTIAL Page 12 03DEC2021

The relationship of trough level of GLS-1027 to serum creatinine relative to treatment group will be examined on an adhoc basis and is outside the scope of this document.

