2.2. Exploratory Objectives

The exploratory objectives are:

- Assess the number of days requiring ICU care relative to treatment group.
- Assess the number of days of NIV, high-flow O2 or mechanical ventilation relative to treatment group.
- Assess incidence of WHO COVID-19 Classification levels relative to baseline serum IL-6 level.
- Assess incidence of WHO COVID-19 Classification levels relative to baseline serum ferritin level.
- Assess incidence of WHO COVID-19 Classification levels relative to baseline CRP
- Assess trough level of GLS-1027 relative to serum creatinine.
- Assess the maximal level of Positive End-Expiratory Pressure (PEEP) for subjects who are intubated relative to treatment group.
- Assess the number of days of PEEP > 5 cm H2O for subjects who are intubated relative to treatment group.
- Assess change in WHO COVID-19 Classification level at Day 28 from enrollment, relative to group.
- Assess SARS-CoV-2 IgM antibody responses relative to treatment group.

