	GLS-1027	GLS-1027	Placebo
	120 mg	360 mg	(N=XX)
	(N=XX)	(N=XX)	· · ·
umber of Days in Hospital			
n	X	x	x
Mean (SD)	xx.xx (xx.xxx)	xx.xx (xx.xxx)	xx.xx (xx.xxx)
Median	x.xx	x.xx	x.xx
Min, Max	xx.x, xx.x	xx.x, xx.x	xx.x, xx.x

Reference: Listing xxxxx

Programming note: Repeat for Table 14.2.2.8.2 Summary of the Number of Days in Hospital (PP Population).

Table 14.2.3.1

Cumulative Incidence of SARS-CoV-2 IgM Antibody Response by Study Day

(PP Population)

Study Day	GLS-1027	GLS-1027	Placebo
Responded	120 mg	120 mg	(N=XX)
	(N=XX)	(N=XX)	`n(%)´
	,	· · · · · · · · · · · · · · · · · · ·	
Day 1			
n	X	X	X
Yes	x (xx.x%)	x (xx.x%)	x (xx.x%)
No	x (xx.x%)	x (xx.x%)	x (xx.x%)
Day 2			
n	X	x	Х
Yes	x (xx.x%)	x (xx.x%)	x (xx.x%)
No	x (xx.x%)	x (xx.x%)	x (xx.x%)
Day 3			
n	X	X	X
Yes	x (xx.x%)	x (xx.x%)	x (xx.x%)
No	x (xx.x%)	x (xx.x%)	x (xx.x%)
Day 4			
n	X	X	X
Yes	x (xx.x%)	x (xx.x%)	x (xx.x%)
No	x (xx.x%)	x (xx.x%)	x (xx.x%)
	(,	~ ()	. (,
••			

The incidence of antibody response is summarized based on results obtained at or prior to the study day. Reference: Listing 16.2.6.3

Table 14.2.4.1
WHO COVID-19 Classification Levels Relative to Baseline Serum Ferritin Level
(PP Population)

			GL	S-1027			GLS-1027								
				L20 mg			360 mg			Placebo			0verall		
WHO Classification	(N=XX)						(N=XX)			(N=XX)		(N=XX)			
Level	Serum Ferritin [1]	Post-Baseline					Post-Baseline			Post-Baseline			Post-Baseline		
	Baseline	Low	N	lormal	High	Low	Normal	High	Low	Normal	High	Low	Normal	High	
5	n	х		х	x	x	х	х	х	х	x	x	х	х	
	Low					XX	XX	XX	XX	XX	XX	XX	XX	XX	
		xx (xx	.x) xx	(xx.x) xx	(xx.x)	(xx.x)	(xx.x)	(xx.x)	(xx.x)	(xx.x)	(xx.x)	(xx.x)	(xx.x)	(xx.)	
	Normal					XX	XX	XX	XX	XX	XX	XX	XX	XX	
		xx (xx	.x) xx	(xx.x) xx	(xx.x)	(xx.x)	(xx.x)	(xx.x)	(xx.x)	(xx.x)	(xx.x)	(xx.x)	(xx.x)	(xx.	
	High					XX	XX	XX	XX	XX	XX	XX	XX	XX	
		xx (xx	.x) xx	(xx.x) xx	(xx.x)	(xx.x)	(xx.x)	(xx.x)	(xx.x)	(xx.x)	(xx.x)	(xx.x)	(xx.x)	(xx.	
6	n	х		х	x	x	х	х	х	х	x	x	х	х	
	Low					XX	XX	XX	XX	XX	XX	XX	XX	XX	
		xx (xx	.x) xx	(xx.x) xx	(xx.x)	(xx.x)	(xx.x)	(xx.x)	(xx.x)	(xx.x)	(xx.x)	(xx.x)	(xx.x)	(xx.	
	Normal					XX	XX	XX	XX	XX	XX	XX	XX	XX	
		xx (xx	.x) xx	(xx.x) xx	(xx.x)	(xx.x)	(xx.x)	(xx.x)	(xx.x)	(xx.x)	(xx.x)	(xx.x)	(xx.x)	(xx.	
	High					XX	XX	XX	XX	XX	XX	XX	XX	XX	
		xx (xx	.x) xx	(xx.x) xx	(xx.x)	(xx.x)	(xx.x)	(xx.x)	(xx.x)	(xx.x)	(xx.x)	(xx.x)	(xx.x)	(xx.	
7	n	х		х	x	x	x	х	х	х	x	x	х	х	
	Low					XX	XX	XX	XX	XX	XX	XX	xx	XX	

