		xx (xx	.x) xx	(xx.x) xx	(xx.x)	(xx.x)	(xx.x)	(xx.x)	(xx.x)	(xx.x)	(xx.x)	(xx.x)	(xx.x)	(xx.	
	Normal					XX	XX	XX	XX	XX	XX	XX	XX	XX	
		xx (xx	.x) xx	(xx.x) xx	(xx.x)	(xx.x)	(xx.x)	(xx.x)	(xx.x)	(xx.x)	(xx.x)	(xx.x)	(xx.x)	(xx.	
	High					XX	XX	XX	XX	XX	XX	XX	XX	XX	
		xx (xx	.x) xx	(xx.x) xx	(xx.x)	(xx.x)	(xx.x)	(xx.x)	(xx.x)	(xx.x)	(xx.x)	(xx.x)	(xx.x)	(xx.	
8	n	х		х	x	x	x	х	х	х	х	х	x	х	
	Low					XX	XX	XX	XX	XX	XX	XX	XX	xx	
		xx (xx	.x) xx	(xx.x) xx	(xx.x)	(xx.x)	(xx.x)	(xx.x)	(xx.x)	(xx.x)	(xx.x)	(xx.x)	(xx.x)	(xx.	
	Normal					XX	XX	XX	XX	XX	XX	XX	XX	XX	
		xx (xx	.x) xx	(xx.x) xx	(xx.x)	(xx.x)	(xx.x)	(xx.x)	(xx.x)	(xx.x)	(xx.x)	(xx.x)	(xx.x)	(xx.	
	High					XX	XX	XX	XX	XX	XX	XX	XX	XX	
		xx (xx	.x) xx	(xx.x) xx	(xx.x)	(xx.x)	(xx.x)	(xx.x)	(xx.x)	(xx.x)	(xx.x)	(xx.x)	(xx.x)	(xx.	

^[1] Worst (most extreme) values presented for serum ferritin.

Reference: Listing xx.x.x.x

date time

Table 14.2.4.2 WHO COVID-19 Classification Levels Relative to Baseline Serum IL-6 Level (PP Population)

			GL	.S-1027			GLS-1027								
				.20 mg			360 mg			Placebo			Overall		
WHO Classification		(N=XX)					(N=XX)			(N=XX)			(N=XX)		
Level	Serum IL-6 [1]		Post-Baseline				Post-Baseline			Post-Baseline			Post-Baseline		
	Baseline	L	.ow N	lormal	High	Low	Normal	High	Low	Normal	High	Low	Normal	High	
5	n		x	x	x	x	x	x	x	x	x	x	x	х	
	Low					XX	XX	XX	XX	XX	XX	XX	XX	XX	
		xx (xx.x) xx	(xx.x) xx	(xx.x)	(xx.x)	(xx.x)	(xx.x)	(xx.x)	(xx.x)	(xx.x)	(xx.x)	(xx.x)	(xx.)	
	Normal					XX	XX	XX	XX	XX	XX	XX	XX	XX	
		xx (xx.x) xx	(xx.x) xx	(xx.x)	(xx.x)	(xx.x)	(xx.x)	(xx.x)	(xx.x)	(xx.x)	(xx.x)	(xx.x)	(xx.)	
	High					XX	XX	XX	XX	XX	XX	XX	xx	XX	
		xx (xx.x) xx	(xx.x) xx	(xx.x)	(xx.x)	(xx.x)	(xx.x)	(xx.x)	(xx.x)	(xx.x)	(xx.x)	(xx.x)	(xx.	
6	n		x	x	x	x	x	x	x	х	x	х	х	х	
	Low					XX	xx	XX	XX	XX	XX	XX	xx	XX	
		xx (xx.x) xx	(xx.x) xx	(xx.x)	(xx.x)	(xx.x)	(xx.x)	(xx.x)	(xx.x)	(xx.x)	(xx.x)	(xx.x)	(xx.	
Norm	Normal	,	•	` ,	` ,	XX	xx	XX	XX	XX	XX	XX	xx	` xx	
		xx (xx.x) xx	(xx.x) xx	(xx.x)	(xx.x)	(xx.x)	(xx.x)	(xx.x)	(xx.x)	(xx.x)	(xx.x)	(xx.x)	(xx.	
	High	`	,	` ,	, ,	XX	`xx´	XX	XX	XX	XX	XX	`xx´	` xx	
	G	xx (xx.x) xx	(xx.x) xx	(xx.x)	(xx.x)	(xx.x)	(xx.x)	(xx.x)	(xx.x)	(xx.x)	(xx.x)	(xx.x)	(xx.	
7	n		x	x	x	x	x	x	х	х	x	х	х	х	
	Low					XX	xx	XX	XX	XX	XX	XX	xx	xx	
		xx (xx.x) xx	(xx.x) xx	(xx.x)	(xx.x)	(xx.x)	(xx.x)	(xx.x)	(xx.x)	(xx.x)	(xx.x)	(xx.x)	(xx.	
	Normal	,	•		, ,	XX	xx	XX	XX	XX	XX	XX	xx	· xx	
		xx (xx.x) xx	(xx.x) xx	(xx.x)	(xx.x)	(xx.x)	(xx.x)	(xx.x)	(xx.x)	(xx.x)	(xx.x)	(xx.x)	(xx.	

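### Tables 14.2.4.1 to 14.2.4.3 show marker shifts within WHO levels 5 to 8, so incidence of WHO levels by baseline IL-6, ferritin or CRP cannot be derived from them

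*SAP*

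**What the plan says.** The objectives are stated the same way in Protocol 2.3 and 8.7 and in SAP 2.2 and 8.3. For IL-6 the SAP has "Assess incidence of WHO COVID-19 Classification levels relative to baseline serum IL-6 level". The other two are "Assess incidence of WHO COVID-19 Classification levels relative to baseline serum ferritin level" and "Assess incidence of WHO COVID-19 Classification levels relative to baseline CRP". In each, the WHO level is the outcome and the baseline marker is the grouping variable.

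SAP 8.4 implements them as "Shift tables for worst (most extreme) values of serum IL-6 level, serum ferritin level, and CRP relative to baseline", which "will be presented for each WHO COVID-19 Classification level". It adds that "No formal statistical analysis is planned" and that these outputs are for the per-protocol (PP) population.

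In SAP Appendix C, the ferritin shell is titled "WHO COVID-19 Classification Levels Relative to Baseline Serum Ferritin Level". It has row blocks for WHO levels 5, 6, 7 and 8. Within each block, baseline low/normal/high is crossed with post-baseline low/normal/high, by arm and overall. The footnote reads "Worst (most extreme) values presented for serum ferritin". The IL-6 and CRP shells are built the same way.

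**The concern.** The table titles name the objective, but the cells answer a different question: how the marker moved, given how ill the patient became. Incidence by baseline category needs, for each category, the number reaching a WHO level divided by everyone in that category. Patients enter at level 3 or 4, so those who never worsen have no row in the shells, and they are an essential part of the denominator.

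At stake are three listed exploratory objectives. Programmed as drawn, the tables would appear under titles promising incidence by baseline marker while giving the reader no means of calculating it.

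**Working it through.** The plan states no figure that could be reproduced here, so the check compares the objective with the shells and then tests whether incidence can be identified.

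**1. What is needed and what is shown**
- Needed: incidence of level L in baseline category c = (patients in c reaching L) / (all patients in c).
- Numerator: summing a baseline row across its post-baseline columns gives patients in c at level L, but only those who also have a post-baseline value. SAP Table 1, footnote d, records these labs only when they were done, so some patients may drop out here.
- Denominator: there is no block below level 5, no total per baseline category and no stated percentage base. The haematology shift shell (Table 14.3.4.3), by contrast, does state its base.
- Elsewhere: Table 14.2.1.1 gives maximum WHO level 6, 7 and 8 by treatment, not by marker. Appendix B lists no other table by baseline marker.

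**2. Identifiability**

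These counts are assumed for illustration and are not from the documents. Take an arm of 44. Fourteen patients reach levels 5 to 8, of whom 10 have high and 4 have normal baseline CRP. The other 30 stay below level 5. The shell is identical however those 30 divide:

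| The 30 below level 5 (high / normal) | Incidence of level 5+, high CRP | Incidence of level 5+, normal CRP |
|---|---|---|
| 5 / 25 | 10/15 = 66.7% | 4/29 = 13.8% |
| 15 / 15 | 10/25 = 40.0% | 4/19 = 21.1% |
| 25 / 5 | 10/35 = 28.6% | 4/9 = 44.4% |

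One set of cells fits a strong positive association, a moderate one and a reversed one.

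**3. Population**

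SAP 6.4 defines PP as safety patients who meet the failure endpoint or are discharged within 14 days without meeting it. A patient still in hospital after Day 14 without failing is in neither group and is dropped. PP therefore selects on the outcome whose incidence is wanted. Adding rows below level 5 in PP alone would not restore the full denominator.

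**4. Rough size**

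Protocol 8.2 plans for 50% on standard of care and 25% on each active dose, with 44 per arm. Applying those rates to level 6 or higher gives 44 × 0.50 + 44 × 0.25 + 44 × 0.25 = 22 + 11 + 11 = 44, and 44/132 = 33%. This is only a proxy: patients whose worst level is 5 would add to it.

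**The case against.** The strongest reply is that the text of SAP 8.4 governs, and it promises every level. If blocks for all levels were produced, and each patient appeared in one block, summing across them would give baseline-category totals. The shells would then merely lag behind the text, and Appendix B allows tables to be reorganised and minor index changes to be made without amendment. Individual results are also to be listed, PP is the prespecified set for exploratory endpoints in both documents, and everything here is descriptive.

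Part of this stands. There is a conflict between text and shell, and following the text would recover much of the denominator. But the totals would cover only PP patients with both a baseline and a post-baseline value. The SAP also does not say whether WHO level in these tables means the maximum, the Day 28 or a per-visit level, so a patient might appear in more than one block. Appendix B's latitude does not supply the missing rows, base or definition, and a listing is not an incidence summary. The exploratory status limits the importance of the point without removing the mismatch.

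**Conclusion.** The concern holds. As drawn, the three tables cannot yield WHO-level incidence by baseline IL-6, ferritin or CRP, and no other planned table does. This follows from the layout and needs no assumed rate. The assumed counts in the illustration show only that even the direction of association is not fixed by the cells.

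Three stronger readings are not supported:
- A reader might infer from the 50% planning rate that half the patients, 66 of 132, are left out. That rate is for the control arm only. In the protocol it concerns level 6 or higher, and in the SAP composite failure, so it is not a rate for levels 5 to 8. The share omitted is unknown, and 44 of 132 reaching the higher levels is a proxy only.
- A reader might infer that the tables carry no information on the objective. Numerators can be recovered from row sums for patients with a post-baseline value. The denominator is what is missing.
- A reader might infer that a regression model is required. The objective is descriptive and the SAP plans no formal analysis, so a correct table is enough.

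The primary endpoint, the safety analyses and the trial's decisions are unaffected. The change is worth making before unblinding because it is cheap.

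**What to change.** In SAP 8.4 and the shells of Tables 14.2.4.1 to 14.2.4.3:
- Tabulate maximum WHO level through Day 28 (4 or lower, 5, 6, 7, 8) by baseline marker category, by arm and overall.
- Give n/N, with N being all patients with a baseline value in that category whether or not a later value exists, and state this base in a footnote.
- Show the number with a missing baseline value for each marker.
- Present the table in ITT beside the prespecified PP version, as Appendix B already does for ICU days, ventilation days and PEEP.
- Keep the shift tables, if wanted, as a separate display with a title that describes a marker shift. Either extend them to every level or amend 8.4 to say which levels are shown.

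The cost is a revised paragraph in 8.4, three rewritten shells and a few index entries. No new data are needed: the baseline markers are collected where performed, and Table 14.2.1.1 already calls for maximum WHO level.
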